# **Clinical Laboratory Tests**

Clinical laboratory tests will be performed at screening (baseline) and after the final image acquisition on the imaging day. Only abnormal laboratory values and RA lab values will be assessed for clinical significance as applicable. For each quantitative laboratory test, summary statistics (mean, standard deviation, median, range, n) on the raw as well as their changes from baseline will be presented by timepoint, by arm, and overall. A shift table will also be produced to show the changes in lab values over time relative to the normal ranges.

If multiple labs were performed at a given visit, then the latest results will be summarized in the analysis tables. All collected lab data will be listed.

#### **Vital Signs**

Vital signs will be performed at screening, just prior to and just after injection. Height and weight will be measured only at screening and will be summarized as part of the baseline and demographic information. For each vital sign (respiration rate, systolic blood pressure, diastolic blood pressure, heart rate and temperature), summary statistics (mean, standard deviation, minimum, maximum, n) on the raw as well as their changes from baseline will be presented by timepoint, by arm, and overall. The baseline value for each of the post-injection vital sign parameters will be the corresponding pre-injection time point. If there are multiple vital signs taken at any time point, then the latest set of vital signs will be used for the analysis. All vital sign data will be listed.

# 6.0 Other Relevant Data Analyses/Summaries

# **6.1 Patient Completion**

A table will be constructed with counts of screen failures and enrolled subjects. Of those enrolled, counts and percentages of patients withdrawing from the study before study completion and the number completing the study will be displayed. For those subjects that withdraw before completion of the study, counts and percentages of the reasons for withdrawal will be tabulated. The table will include summary counts and percentages by study arm and overall. A data listing of all subject completion and withdrawal data will also be constructed.

#### 6.2 Physical Exam

Physical exams will be performed at screening. All physical exam data will be listed.

#### **6.3 Study Drug Administration**

The volume, the calculated mass dose, and radioactivity of Tc 99m tilmanocept injected will be summarized by arm and overall. All study drug administration data will be listed.

#### 6.4 RA Evaluation

Each RA subject will undergo a DAS28 evaluation during screening. The swollen and tender joints will be identified and documented during the physical examination. Results of all DAS28 evaluations will be listed.

#### 6.5 Concomitant Medications

Prior and concomitant medications will be collected for 30 days prior to Day 0, and all RA medications will be collected for 6 months prior to Day 0. All prior and concomitant medications will be listed, as shown in Appendix B. A separate data listing will be created to show only those medications that were taken for RA within the 6 months prior to Day 0 injection.

# 7.0 List of Analysis Tables, Figures and Listings

Table No.	Table Title	Included in Final Tables	Shown in Appendix B
1	Subject Disposition by Study Arm	X	X
2	Demographics and Baseline Data Summary Statistics by Arm – Continuous Variables (Safety Population)	Х	Х
3	Demographics and Baseline Data Summary Statistics by Arm – Categorical Variables (Safety Population)	Х	Х
4	Summary of Study Drug Administration by Arm (Safety Population)	Х	Х
5	Summary of TUV joint on both Arms Per Reader, Joint, and View (ITD population)	Х	Х
6	Summary of TUV joint on both Arms Per Reader, Joint, and View (PP Population)	Х	
7	Summary of SUV on Arm 2 per Joint and a Total of All Joints (ITD population)	Х	Х
8	Summary of SUV on Arm 2 per Joint and a Total of All Joints (PP Population)	Х	
9	Normal Range of TUV joint for the Three Blinded Readers in All Arm 1 and 2 Healthy Control Subjects (ITD Population)	Х	Х
10	Normal Range of TUV joint for the Three Blinded Readers in All Arm 1 and 2 Healthy Control Subjects (PP Population)	Х	
11	Correlation Between TUV joint and Age and BMI – All Arm 1 and 2 Healthy Control Subjects (ITD Population)	Х	Х
12	Correlation Between TUV joint and Age and BMI – All Arm 1 and 2 Healthy Control Subjects (PP Population)	Х	
13	Frequency Counts and Percentage of Localization in SPECT/ CT Imaging in RA Subjects (ITD Population)	Х	Х
14	Frequency Counts and Percentage of Localization in SPECT/ CT Imaging in RA Subjects (PP Population)	Х	
15	Shapiro-Wilk P-Value for Normality Test for TUV joint Data – All Arm 1 and 2 Healthy Control Subjects (ITD Population)	Х	Х
16	Shapiro-Wilk P-Value for Normality Test for TUV joint Data – All Arm 1 and 2 Healthy Control Subjects (PP Population)	Х	
17	Predictive Value of Planar Scans for SPECT/CT Per Joint and Reader (ITD Population)	Х	Х
18	Predictive Value of Planar Scans for SPECT/CT Per Joint and Reader (PP Population)	Х	
19	Number and Percentage of Subjects with TEAEs (Safety Population)	Х	Х
20	Summary of TEAEs (Safety Population)	Х	Х
21	Number and Percentage of Subjects with TESAEs (Safety Population)	Х	Х
22	Number and Percentage of Subjects With TEAEs by Severity Grade (Safety Population)	Х	Х
23	Number and Percentage of Subjects With TEAEs by Level of Relationship to Tc 99m Tilmanocept (Safety Population)	Х	Х
24	Number and Percentage of Subjects With TEAEs by Level of Relationship to Procedure (Safety Population)	Х	

Table No.	Table Title	Included in Final Tables	Shown in Appendix B
25	Serum Chemistry Clinical Laboratory Parameters Summary Statistics by Arm (Safety Population)	X	X
26	Hematology Clinical Laboratory Parameters Summary Statistics by Arm (Safety Population)	X	
27	Urinalysis Clinical Laboratory Parameters Summary Statistics by Arm (Safety Population)	X	
28	Serum Chemistry Clinical Laboratory Parameters Shift Table by Arm (Safety Population)	Х	Х
29	Hematology Clinical Laboratory Parameters Shift Table by Arm (Safety Population)	Х	
30	Urinalysis Clinical Laboratory Parameters Shift Table by Arm (Safety Population)	Х	
31	Vital Signs Summary Statistics by Arm (Safety Population)	Χ	Х

Figure No.	Figure Title	Included in Final Figures	Shown in Appendix B
Fig1	Normal QQ plot for TUV joint Data – All Arm 1 and 2 Healthy Control Subjects (ITD Population)	Х	X
Fig2	Normal QQ plot for TUV joint Data – All Arm 1 and 2 Healthy Control Subjects (PP Population)	Х	
Fig3	Scatter Plot of TUV joint Distribution of the Right Hand – All Arm 1 and 2 Healthy Control Subjects (ITD Population)	Х	Х
Fig4	Scatter Plot of TUV joint Distribution of the Right Hand – All Arm 1 and 2 Healthy Control Subjects (PP Population)	Х	
Fig5	Scatter Plot of TUV joint Distribution of the Left Hand – All Arm 1 and 2 Healthy Control Subjects (ITD Population)	Х	Х
Fig6	Scatter Plot of TUV joint Distribution of the Left Hand – All Arm 1 and 2 Healthy Control Subjects (PP Population)	Х	
Fig7	Scatter Plot of TUV joint Distribution for MCP1 by Age – All Arm 1 and 2 Healthy Control Subjects (ITD Population)	Х	Х
Fig8	Scatter Plot of TUV joint Distribution for MCP1 by Age – All Arm 1 and 2 Healthy Control Subjects (PP Population)	Х	
Fig9	Scatter Plot of TUV joint Distribution for MCP2 by Age – All Arm 1 and 2 Healthy Control Subjects (ITD Population)	Х	
Fig10	Scatter Plot of TUV joint Distribution for MCP2 by Age – All Arm 1 and 2 Healthy Control Subjects (PP Population)	Х	
Fig11	Scatter Plot of TUV joint Distribution for MCP3 by Age – All Arm 1 and 2 Healthy Control Subjects (ITD Population)	Х	
Fig12	Scatter Plot of TUV joint Distribution for MCP3 by Age – All Arm 1 and 2 Healthy Control Subjects (PP Population)	Х	
Fig13	Scatter Plot of TUV joint Distribution for MCP4 by Age – All Arm 1 and 2 Healthy Control Subjects (ITD Population)	Х	
Fig14	Scatter Plot of TUV joint Distribution for MCP4 by Age – All Arm 1 and 2 Healthy Control Subjects (PP Population)	Х	
Fig15	Scatter Plot of TUV joint Distribution for MCP5 by Age – All Arm 1 and 2 Healthy Control Subjects (ITD Population)	Х	

Figure		Included in Final	Shown in Appendix
No.	Figure Title	Figures	В
Fig16	Scatter Plot of TUV joint Distribution for MCP5 by Age – All Arm 1	Х	
	and 2 Healthy Control Subjects (PP Population)		
Fig17	Scatter Plot of TUV joint Distribution for PIP1 by Age – All Arm 1	X	
	and 2 Healthy Control Subjects (ITD Population)		
Fig18	Scatter Plot of TUV joint Distribution for PIP1 by Age – All Arm 1	X	
	and 2 Healthy Control Subjects (PP Population)		
Fig19	Scatter Plot of TUV joint Distribution for PIP2 by Age – All Arm 1	Х	
	and 2 Healthy Control Subjects (ITD Population)		
Fig20	Scatter Plot of TUV joint Distribution for PIP2 by Age – All Arm 1	X	
	and 2 Healthy Control Subjects (PP Population)		
Fig21	Scatter Plot of TUV joint Distribution for PIP3 by Age – All Arm 1	X	
	and 2 Healthy Control Subjects (ITD Population)		
Fig22	Scatter Plot of TUV joint Distribution for PIP3 by Age – All Arm 1	X	
	and 2 Healthy Control Subjects (PP Population)		
Fig23	Scatter Plot of TUV joint Distribution for PIP4 by Age – All Arm 1	X	
	and 2 Healthy Control Subjects (ITD Population)		
Fig24	Scatter Plot of TUV joint Distribution for PIP4 by Age – All Arm 1	X	
	and 2 Healthy Control Subjects (PP Population)		
Fig25	Scatter Plot of TUV joint Distribution for PIP5 by Age – All Arm 1	X	
	and 2 Healthy Control Subjects (ITD Population)		
Fig26	Scatter Plot of TUV joint Distribution for PIP5 by Age – All Arm 1	X	
	and 2 Healthy Control Subjects (PP Population)		
Fig27	Scatter Plot of TUV joint Distribution for Wrist by Age – All Arm 1	Х	
	and 2 Healthy Control Subjects (ITD Population)		
Fig28	Scatter Plot of TUV joint Distribution for Wrist by Age – All Arm 1	Х	
	and 2 Healthy Control Subjects (PP Population)		
Fig29	Scatter Plot of TUV joint Distribution by Sex – All Arm 1 and 2	X	
	Healthy Control Subjects (ITD Population)		
Fig30	Scatter Plot of TUV joint Distribution by Sex – All Arm 1 and 2	X	
	Healthy Control Subjects (PP Population)		
Fig31	Scatter Plot of TUV joint Distribution by BMI – All Arm 1 and 2	X	
	Healthy Control Subjects (ITD Population)		
Fig32	Scatter Plot of TUV joint Distribution by BMI – All Arm 1 and 2	Х	
	Healthy Control Subjects (PP Population)		
Fig33	Scatter Plot of Residuals by Age – All Arm 1 and 2 Healthy	X	X
	Control Subjects (ITD Population)		
Fig34	Scatter Plot of Residuals by Age – All Arm 1 and 2 Healthy	X	
	Control Subjects (PP Population)		

Listing No.	Data Listing Title	Included in Final Listings	Shown in Appendix B
DL1	Subject Disposition Data Listing	X	X
DL2	Inclusion/Exclusion Data Listing	Х	Х
DL3	Protocol Deviations Data Listing	Х	Х
DL4	Demographics Data Listing	Х	Х

Listing No.	Data Listing Title	Included in Final Listings	Shown in Appendix B
DL5	Subjects Excluded from ITD Population Data Listing	X	X
DL6	Subjects Excluded from PP Population Data Listing	X	X
DL7	Subjects Excluded from Safety Population Data Listing	X	X
DL8	Medical History Data Listing	X	Х
DL9	Prior and Concomitant Medications Data Listing	X	Х
DL10	Prior and Concomitant RA Medications Data Listing	Х	Х
DL11	Adverse Events Data Listing	Х	Х
DL12	Subject Laboratory Profiles – Hematology Data Listing	Х	Х
DL13	Subject Laboratory Profiles – Serum Chemistry Data Listing	Х	
DL14	Subject Laboratory Profiles – Urinalysis Data Listing	Х	
DL15	Subject Laboratory Profiles – Rheumatology Panel Data Listing	Х	
DL16	Physical Exam Data Listing	Х	Х
DL17	ACR/EULAR 2010 Classification Data Listing	Х	Х
DL18	DAS-28 by Joint Data Listing – Arm 2 RA Subjects	Х	Х
DL19	DAS-28 by Subject Data Listing – Arm 2 RA Subjects	Х	Х
DL20	Vital Signs Data Listing	Х	Х
DL21	Study Drug Administration Data Listing	Х	Х
DL22	Post-Injection Imaging Data Listing	Х	Х
DL23	SPECT/CT Reader Results Data Listing – Hands and Wrists	Х	Х
DL24	TUV Data Listing	Х	Х

# **Appendix A – Tables, Figures and Listing Specifications**

#### Orientation

Tables and figures will be displayed in landscape.

#### **Margins**

Margins will be 1 inch on all sides. Table and listing boundaries will not extend into the margins.

#### **Font**

Courier New, 8 point.

#### Headers

The table number will be on the first line of the title. The title area will contain the Sponsor name, the study number, and the name of the table. The title area will contain the page number (Page x of y) on the far right, 1 line above the name of the table.

#### **Footers**

- The first line will be a solid line.
- Next will be any footnotes regarding information displayed in the table.
- Below these footnotes will be displayed "STATKING Clinical Services (DD-MMM-YYYY)" on the far left.
- The last line will display the name of the SAS program that generated the table and (if applicable) the source data reference.

## **Table Disclaimer**

The format of the mock tables shown in the appendix of this SAP will be the format of the deliverable tables to the extent that Word document constructed tables can match production tables produced by SAS. This formatting includes the content and format of the header and footer areas of the tables. The Sponsor agrees to the format of the tables as shown in the appendix.

Further programming charges will be applicable for changes in the format of tables (including title statements, notes, data dependent footnotes, etc.) made after the approval of the SAP.

# **Missing Values**

All missing values will be displayed on the output tables/listings as blanks.

# **Display of Study Dates**

The date format to be used is dd-mmm-yyyy. Missing parts of dates are not shown (i.e., for a missing day value, the value displayed is in yyyy-mm format).

# Appendix B – Table Shells

Table 1. Subject Disposition by Study Arm Navidea Biopharmaceuticals - Study No. NAV3-35

		HC-1	HC-2	RA	Overall
		(N = xxx)	(N = xxx)	(N = xxx)	(N = xxx)
Screen Failures					XX
Enrolled		xxx	xxx	xxx	xxx
Completed		xx (xxx%)	xx (xxx%)	xx (xxx%)	xx (xxx%)
Withdrawn		xx (xxx%)	xx (xxx%)	xx (xxx%)	xx (xxx%)
Withdrawal Reason	Adverse Event	xx (xxx%)	xx (xxx%)	xx (xxx%)	xx (xxx%)
	Protocol Violation Lost to Follow Up	xx (xxx%)	xx (xxx%)	xx (xxx%)	xx (xxx%)
	Withdrawal of Consent	xx (xxx%)	xx (xxx%)	xx (xxx%)	xx (xxx%)
	Sponsor Discretion	xx (xxx%)	xx (xxx%)	xx (xxx%)	xx (xxx%)
	Investigator Discretion	xx (xxx%)	xx (xxx%)	xx (xxx%)	xx (xxx%)
	Death	xx (xxx%)	xx (xxx%)	xx (xxx%)	xx (xxx%)
	Other	xx (xxx%)	xx (xxx%)	xx (xxx%)	xx (xxx%)

<sup>a HC-1 = healthy control-Arm 1, HC-2 = healthy control-Arm 2, RA = rheumatoid arthritis (stable treatment regimen; Arm 2) The denominator for all percentages in the table is the number of enrolled subjects in the respective arm and overall. STATKING Clinical Services (DD-MMM-YYYY)
Source Program: xxxxxxx.sas

Table 2. Demographics and Baseline Data Summary Statistics by Arm - Continuous Variables Navidea Biopharmaceuticals - Study No. NAV3-35 Safety Population (N=xxx)

Variable	Arma	Mean	Std Dev	n	Min	Max	Median
Age (years)	HC-1	XXX	XXX	XXX	XXX	XXX	XXX
	HC-2	XXX	XXX	XXX	XXX	XXX	XXX
	RA	XXX	XXX	XXX	XXX	XXX	XXX
Height (inches)	HC-1	XXX	XXX	XXX	XXX	XXX	XXX
	HC-2	XXX	XXX	XXX	XXX	XXX	XXX
	RA	XXX	XXX	XXX	XXX	XXX	XXX
Weight (pounds)	HC-1	XXX	XXX	XXX	XXX	XXX	XXX
	HC-2	XXX	XXX	XXX	XXX	XXX	XXX
	RA	XXX	XXX	XXX	XXX	XXX	XXX
BMI (kg/m^2)	HC-1	XXX	XXX	XXX	XXX	XXX	XXX
	HC-2	XXX	XXX	XXX	XXX	XXX	XXX
	RA	XXX	XXX	XXX	XXX	XXX	XXX

<sup>a HC-1 = healthy control-Arm 1, HC-2 = healthy control-Arm 2, RA = rheumatoid arthritis (stable treatment regimen; Arm 2) STATKING Clinical Services (DD-MMM-YYYY) Source Program: xxxxxxx.sas

Table 3. Demographics and Baseline Data Summary Statistics by Arm - Categorical Variables

Navidea Biopharmaceuticals - Study No. NAV3-35

Safety Population (N= xxx)

			Arma	
		HC-1	HC -2	RA
Variable	Category	(N= xxx)	(N= xxx)	(N= xxx)
Gender	Male	vvv (vvv%)	vvv (vvv%)	vvv (vvv%)
Gender		xxx (xxx%)	xxx (xxx%)	xxx (xxx%)
	Female With Childbearing Potential	xxx (xxx%)	xxx (xxx%)	xxx (xxx%)
	Female With No Childbearing Potential	xxx (xxx%)	xxx (xxx%)	xxx (xxx%)
Race	American Indian or Alaska Native	xxx (xxx%)	xxx (xxx%)	xxx (xxx%)
	Asian	xxx (xxx%)	xxx (xxx%)	xxx (xxx%)
	Black or African American	xxx (xxx%)	xxx (xxx%)	xxx (xxx%)
	Native Hawaiian or Other Pacific Islander	xxx (xxx%)	xxx (xxx%)	xxx (xxx%)
	White	xxx (xxx%)	xxx (xxx%)	xxx (xxx%)
	Other			
Ethnicity	Hispanic or Latino	xxx (xxx%)	xxx (xxx%)	xxx (xxx%)
2	Not Hispanic or Latino	xxx (xxx%)	xxx (xxx%)	xxx (xxx%)
II	Dialet Hended	/		(° )
Handedness	Right Handed	xxx (xxx%)	xxx (xxx%)	xxx (xxx%)
	Left Handed	xxx (xxx%)	xxx (xxx%)	xxx (xxx%)
	Ambidextrous	xxx (xxx%)	xxx (xxx%)	xxx (xxx%)

a HC-1 = healthy control-Arm 1, HC-2 = healthy control-Arm 2, RA = rheumatoid arthritis (stable treatment regimen; Arm 2) STATKING Clinical Services (DD-MMM-YYYY) Source Program: xxxxxxx.sas

Table 4. Summary of Study Drug Administration by Arm
Navidea Biopharmaceuticals - Study No. NAV3-35
Safety Population (N= xxx)

	Arma	Mean	Std Dev	n	Min	Max	Median
Tc 99m Dose (mCi)	HC-1	XXXX	XXXX	XX	XXXX	XXXX	XXXX
	HC-2	XXXX	XXXX	XX	XXXX	XXXX	XXXX
	RA	XXXX	XXXX	XX	XXXX	XXXX	XXXX
Mass Dose (µg)	HC-1	xxxx	XXXX	xx	xxxx	xxxx	xxxx
(r.g)	HC-2	XXXX	xxxx	XX	XXXX	XXXX	XXXX
	RA	XXXX	xxxx	XX	XXXX	XXXX	XXXX
Total Volume of Tc 99m Tilmanocept Injected (mL)	HC-1	XXXX	XXXX	XX	XXXX	XXXX	XXXX
	HC-2	XXXX	XXXX	XX	XXXX	XXXX	XXXX
	RA	XXXX	XXXX	XX	XXXX	XXXX	XXXX

<sup>a HC-1 = healthy control-Arm 1, HC-2 = healthy control-Arm 2, RA = rheumatoid arthritis (stable treatment regimen; Arm 2) STATKING Clinical Services (DD-MMM-YYYY) Source Program: xxxxxxx.sas

Page x of y

Table 5. Summary of TUVjoint on both Arms Per Reader, Joint, and View
Navidea Biopharmaceuticals - Study No. NAV3-35

ITD Population (N=xxx)

Arma	Reader	View	Joint	Mean	Std Dev	n	Min	Max	Median
XXXX	xxxxxxxxxxxx	XXXXXXXX	XX	XXXX.X	XXXX.X	XXX	XXXX.X	XXXX.X	XXXX.X
		XXXXXXXX	XX	XXXX.X	XXXX.X	XXX	XXXX.X	XXXX.X	XXXX.X
		XXXXXXXX	XX	XXXX.X	XXXX.X	XXX	XXXX.X	XXXX.X	XXXX.X
		XXXXXXXX	XX	XXXX.X	XXXX.X	XXX	XXXX.X	XXXX.X	XXXX.X
	XXXXXXXXXXXXXXX	XXXXXXXX	XX	XXXX.X	XXXX.X	xxx	xxxx.x	XXXX.X	xxxx.x
		XXXXXXXX	XX	XXXX.X	XXXX.X	xxx	xxxx.x	XXXX.X	xxxx.x
		XXXXXXXX	XX	XXXX.X	XXXX.X	XXX	XXXX.X	XXXX.X	XXXX.X
		XXXXXXXX	XX	XXXX.X	XXXX.X	xxx	xxxx.x	XXXX.X	XXXX.X
XXXX	XXXXXXXXXXXXXXX	XXXXXXXX	XX	XXXX.X	XXXX.X	xxx	xxxx.x	XXXX.X	xxxx.x
		XXXXXXXX	XX	XXXX.X	XXXX.X	XXX	XXXX.X	XXXX.X	XXXX.X
		XXXXXXXX	XX	XXXX.X	XXXX.X	xxx	xxxx.x	XXXX.X	XXXX.X
		XXXXXXXX	XX	XXXX.X	XXXX.X	XXX	XXXX.X	XXXX.X	XXXX.X
	xxxxxxxxxxxxx	XXXXXXXX	XX	XXXX.X	XXXX.X	XXX	XXXX.X	XXXX.X	XXXX.X
		XXXXXXXX	XX	XXXX.X	XXXX.X	XXX	XXXX.X	XXXX.X	XXXX.X
		XXXXXXXX	XX	XXXX.X	XXXX.X	XXX	XXXX.X	XXXX.X	XXXX.X
		XXXXXXXX	XX	XXXX.X	XXXX.X	XXX	XXXX.X	XXXX.X	XXXX.X

Table format is repeated for the PP population.

a HC-1 = healthy control-Arm 1, HC-2 = healthy control-Arm 2, RA = rheumatoid arthritis (stable treatment regimen; Arm 2) STATKING Clinical Services (DD-MMM-YYYY) Source Program: xxxxxxx.sas

Page x of y

Table 7. Summary of SUV on Arm 2 per Joint and Total of All Joints
Navidea Biopharmaceuticals - Study No. NAV3-35

ITD Population (N=xxx)

Arm 2ª	Joint	Mean	Std Dev	n	Min	Max	Median
HC-2	XX	XXXX.X	XXXX.X	XXX	XXXX.X	XXXX.X	XXXX.X
	XX	XXXX.X	XXXX.X	XXX	XXXX.X	XXXX.X	XXXX.X
	XX	XXXX.X	XXXX.X	XXX	XXXX.X	XXXX.X	XXXX.X
	XX	XXXX.X	XXXX.X	XXX	XXXX.X	XXXX.X	XXXX.X
	XX	XXXX.X	XXXX.X	XXX	XXXX.X	XXXX.X	XXXX.X
	XX	XXXX.X	XXXX.X	XXX	XXXX.X	XXXX.X	XXXX.X
	XX	XXXX.X	XXXX.X	XXX	XXXX.X	XXXX.X	XXXX.X
	Total of All	XXXX.X	XXXX.X	XXX	XXXX.X	XXXX.X	XXXX.X
	Joints						
RA	XX	XXXX.X	XXXX.X	XXX	XXXX.X	XXXX.X	XXXX.X
	XX	XXXX.X	XXXX.X	XXX	XXXX.X	XXXX.X	XXXX.X
	XX	XXXX.X	XXXX.X	XXX	XXXX.X	XXXX.X	XXXX.X
	XX	XXXX.X	XXXX.X	XXX	XXXX.X	XXXX.X	XXXX.X
	XX	XXXX.X	XXXX.X	XXX	XXXX.X	XXXX.X	xxxx.x
	XX	XXXX.X	XXXX.X	XXX	XXXX.X	xxxx.x	xxxx.x
	XX	XXXX.X	XXXX.X	XXX	xxxx.x	XXXX.X	xxxx.x
	Total of All	XXXX.X	XXXX.X	XXX	XXXX.X	xxxx.x	xxxx.x
	Joints						

Table format is repeated for the PP population.

a HC-2 = healthy control-Arm 2, RA = rheumatoid arthritis (stable treatment regimen; Arm 2)
STATKING Clinical Services (DD-MMM-YYYY)
Source Program: xxxxxxx.sas

Page x of y

Table 9. Normal Range of  $TUV_{joint}$  for the Three Blinded Readers in All Arm 1 and 2 Healthy Control Subjects

Navidea Biopharmaceuticals - Study No. NAV3-35

ITD Population (N=xxx)

Joint	View	Reader	Number of Joints	Mean	Standard Deviation	Estimated 5 %tile	Estimated 95 %tile
xxxxxxxxxx	xx	xx	xxx	xxx.xx	xx.xxx	xx.xxx	xx.xx
		xx	xxx	xxx.xx	xx.xx	xx.xxx	xx.xx
		xx	xxx	xxx.xx	xx.xx	xx.xxx	xx.xx
	XX	xx	xxx	xxx.xx	XX.XXX	xx.xxx	xx.xxx
		xx	xxx	xxx.xx	xx.xxx	xx.xxx	xx.xxx
		XX	xxx	xxx.xx	xx.xxx	xx.xxx	xx.xxx

If there are no major protocol deviations, then analysis tables for the ITD and PP populations will contain identical results. STATKING Clinical Services (DD-MMM-YYYY)

Source Program: xxxxxxx.sas

#### Table format is repeated for the PP population

Page x of y

Table 11. Correlation Between  $TUV_{joint}$  and Age and BMI - All Arm 1 and 2 Healthy Control Subjects Navidea Biopharmaceuticals - Study No. NAV3-35 ITD Population (N=xxx)

Variable	TUV	P-value a
AGE	xx.xxx	x.xxx
BMI	xx.xxx	x.xxxx

# Table format is repeated for the PP population

<sup>a P-value testing H0: Correlation Coefficient = 0 vs H1: Correlation Coefficient ≠ 0. STATKING Clinical Services (DD-MMM-YYYY) Source Program: xxxxxxx.sas

Page x of y

Table 13. Frequency Counts and Percentage of Localization in SPECT/CT Imaging in RA Subjects
Navidea Biopharmaceuticals - Study No. NAV3-35

ITD Population (N=xxx)

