#### 1.3 Sample Size

The study will enroll up to 135 evaluable subjects in Arms 1 and 2 allocated below, imaged at up to 8 study centers.

Arm 1 will have up to N = 120 evaluable HC subjects, Arm 2 will have up to N = 15 evaluable subjects; 5 HCs and 10 RA subjects.

A subject is considered evaluable if he/she meets the criteria for the analysis population and has the data necessary for computing the primary endpoint(s) relevant to his/her study Arm.

The sample will be stratified 3:1, females to males ratio to reflect RA incidence in the United States. The sex-specific samples will be further stratified by age to reflect the Census estimated US population in 2019.

The target sample sizes are given below.

Age Range	Male	Female	Total
30 to 39 years	8	23	31
40 to 49 years	7	21	28
50 to 59 years	8	22	30
60 to 69 years	7	21	28
70 years and older	6	21	27
Total	36	108	144

An effort will be made to target enrollment in this group to include 2 men and 8 women 80 years old and over.

The existing data for HC subjects was used in a bootstrap procedure to evaluate the width of 95% confidence intervals for the 95 percentiles for various sample sizes. The sponsor has decided for its business purposes that knowing the percentile to within 0.05 of its true value is sufficient. A sample of size N = 144 HC results (this includes the subjects from Arm 1 of NAV3-31) in 95% confidence intervals with half-widths less than 0.05.

The sample size for Arm 2 was determined to be sufficient for the business purposes of the sponsor. The sample size for Arm 2 will be 5 HCs and 10 RA subjects.

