### 4.2.2 Analysis of Secondary Efficacy Variables

Healthy Controls in Both Arms 1 and 2:

Normal quantile plots will be provided per-joint and reader, along with the p-value for the Shapiro-Wilk test of Normality.

Scatter plots of  $TUV_{joint}$  by age per-joint will be provided, along with the correlation coefficients and p-values. The hypotheses for the p-value to test the correlation coefficient are:  $H_0$ :  $\rho = 0$  vs  $H_1$ :  $\rho \neq 0$ , where  $\rho$  is the correlation coefficient. The p-value evaluating age in the regression model will be provided in the figure.

Scatter plots of  $TUV_{joint}$  by BMI will be provided, along with the correlation coefficients and p-values. The hypotheses for the p-value to test the correlation coefficient are:  $H_0$ :  $\rho = 0$  vs  $H_1$ :  $\rho \neq 0$ , where  $\rho$  is the correlation coefficient. The p-value evaluating BMI in the regression model will be provided in the figure.

Scatter plots of TUVjoint by sex will be provided.

To check the relationship between the variance of TUVjoint and age, a quantile regression model will be fitted with an intercept as a fixed term. The plot of the residuals on the y-axis and age on the x-axis will be provided.

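### The age, BMI and sex relationships with TUVjoint are to be judged by correlations, p-values and plots, with an undefined regression model and no effect size or interval in TUV units

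*SAP*

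**What the plan says.** SAP 4.1.2 lists, for the healthy controls of both arms, the relationship of TUVjoint with age (by joint), with sex and with BMI. SAP 4.2.2 sets out the analyses:

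- **Age:** scatter plots per joint, a correlation coefficient and a p-value for zero correlation. It adds: "The p-value evaluating age in the regression model will be provided in the figure".
- **BMI:** the same scheme, with: "The p-value evaluating BMI in the regression model will be provided in the figure".
- **Sex:** "Scatter plots of TUV joint by sex will be provided", and nothing more.

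The Table 11 shell in SAP Appendix B (repeated as Table 12 for the per-protocol population) has one row for age and one for BMI. Each holds a coefficient and a p-value, with the footnote "P-value testing H0: Correlation Coefficient = 0 vs H1: Correlation Coefficient" (nonzero). There is no sex row, slope or interval, and no split by joint, view or reader.

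Neither document states which correlation coefficient is meant or which terms the regression contains. The only regressions with stated terms are the quantile regression for the primary limits and the one for variance against age, where "a quantile regression model will be fitted with an intercept as a fixed term". Both contain an intercept only.

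**The concern.** The study builds a normative database from controls sampled by age and sex, and its primary limits pool all of them. These secondary analyses are therefore its planned evidence on whether one normal limit suits all healthy adults. That is a question of size: by how much does TUVjoint shift across the adult age range, across BMI, or between women and men?

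A correlation and a p-value do not answer it. A small p-value may go with a trivial shift, and a large one may be read as no relationship when the data are compatible with a shift of practical importance. For sex, no estimate is planned at all. Because the regression model is not written down, two programmers could put different p-values on the same figure.

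**Working it through.** The documents give no power, alpha or effect size for these analyses, so there is no planned figure to reproduce.

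**Inputs.** Healthy controls: up to 120 in Arm 1 plus 5 in Arm 2 = 125 (SAP 1.3). Age: target strata of SAP 1.3 (31, 28, 30, 28, 27), taken as uniform within bands with the oldest band assumed to be 70-85, giving mean 54.9 and SD 15.17 years. Two-sided 5% tests and one value per subject are assumed. The SD of TUVjoint is not in the documents, so a range of 0.05 to 0.20 is used. Within it, 0.145 is the Normal-theory SD at which the 95th percentile has half-width 0.05 with N = 144: 1.96 x sqrt(0.05 x 0.95/144)/0.1031 = 0.345, and 0.05/0.345 = 0.145. The plan states half-widths below 0.05, so on that formula 0.145 is an upper value.

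**1. What the regression p-value adds.** For Pearson correlation and a one-covariate linear regression, the two p-values agreed to about 2e-15 over 2,000 simulated datasets. Under other readings they differ. In one simulated dataset Pearson and simple regression gave 0.0023, Spearman 0.0062, median regression 0.0044, and linear regression on age and BMI together 0.088.

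**2. What a significant correlation conveys.** With t = 1.979 on 123 df, the smallest significant correlation is 1.979/sqrt(123 + 1.979^2) = 0.176. The slope per decade is 0.176 x SD/15.17 x 10, which is 0.006 TUV at SD 0.05 and 0.023 at SD 0.20. The same correlation and p-value cover a four-fold range of effects.

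**3. What a non-significant result excludes.** For the change between ages 35 and 75, SE = 40 x SD/(15.17 x sqrt(124)), with SD taken about the trend line. The 95% half-width is 1.979 x SE. For a true rise of 0.05, the chance of p > 0.05 is approximately Phi(1.979 - 0.05/SE).

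| SD | SE | 95% half-width | Non-significant, formula | Non-significant, simulated |
|---|---|---|---|---|
| 0.05 | 0.012 | 0.023 | 1% | 2% |
| 0.10 | 0.024 | 0.047 | 45% | 46% |
| 0.145 | 0.034 | 0.068 | 70% | 69% |
| 0.20 | 0.047 | 0.094 | 82% | 81% |

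At the larger SDs, an interval would show that the question is unresolved.

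**4. One at a time or together.** Assume TUV depends on BMI only. The induced age-TUV correlation is the product of the age-BMI and BMI-TUV correlations. At 0.2 and 0.4 the unadjusted age test is significant in 14% of studies; at 0.3 and 0.4, in 27%. It is 5% if age and BMI are uncorrelated. With age and BMI in one model it is about 5% throughout. The documents give none of these correlations.

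**5. Two hands.** The limits are defined for bilateral joints and the Table 9 shell counts joints, which suggests that left and right are pooled. If both hands enter as independent values with left-right correlation c, the nominal 5% test rejects with probability 2 x [1 - Phi(1.96/sqrt(1 + c))]: 8.6% at c = 0.3 and 15.5% at c = 0.9 (c assumed).

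**The case against.** Several arguments limit this point.

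- **Redundancy.** A reader might infer that the regression p-value simply repeats the correlation test. The SAP does not establish this. It holds for Pearson with one linear covariate, the simplest reading, but neither is stated. The supportable defect is that the model is undefined.
- **False age effects.** A reader might treat the 14% and 27% above as false positives. They are not, because the stated null is zero correlation and in those scenarios it is false. If TUV rises with BMI and BMI with age, older healthy adults do have higher values. With correlations 0.3 and 0.4, about 6.9% of the oldest fifth exceed the pooled 95th percentile, against 3.4% of the youngest fifth. The unadjusted trend is what bears on a single limit. Adjustment helps only to explain its source.
- **The 0.05 tolerance.** The sponsor's statement, "knowing the percentile to within 0.05 of its true value is sufficient", sets precision for a percentile, not a margin for a shift in the mean. Nor does adding covariates cure low power; only the interval helps interpretation.
- **Consequence.** No planned decision uses Tables 11 and 12, and these endpoints are absent from protocol 9.3. The age plots show the trend on the TUV scale, and a slope could be roughly back-calculated from a correlation and two SDs. But Table 11 is not split by joint, view or reader, Table 2 gives the age SD by arm, and no interval would follow directly.

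All this narrows the point. It does not supply the missing estimates or define the model.

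**Conclusion.** The concern holds as one of specification and reporting. Three relationships are named as secondary endpoints. Two are answered by a correlation and p-value and one by a picture, with an undefined regression and no effect size or interval in TUV units. The size of each relationship, and whether a non-significant result excludes a meaningful trend, cannot be judged from the planned output.

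How much this matters depends on the TUV SD, which the documents do not give. The chance of missing a 0.05 rise over 40 years runs from about 1-2% to 82% across the assumed SDs, so no single figure in that range should be quoted alone. The documents do not support a claim that the age test is invalid, and the primary 5th and 95th percentile limits are not affected.

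**What to change.** In SAP 4.2.2, state the type of correlation and replace the undefined regression by a linear regression of TUVjoint for each joint, view and reader. Use one value per subject (the left-right mean) or standard errors clustered by subject.

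In Tables 11 and 12, report for each variable:

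- the unadjusted coefficient, which bears on whether one limit fits all healthy adults;
- the coefficient from a model with age, BMI and sex together, which helps to explain the source of a trend.

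Express them per 10 years, per 5 kg/m2 and as female minus male, each with a 95% confidence interval. Label the results descriptive: 11 joints x 2 views x 3 readers = 66 combinations, so about 66 x 0.05 = 3.3 nominally significant results per variable are expected with no relationship at all. Use 0.05 TUV only as an informal yardstick. Keep the scatter plots and correlations.

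The cost is SAP wording, a short regression program and longer tables: 66 x 3 = 198 coefficients per model and population. Age, sex, height and weight are already collected, and BMI is already in the Table 2 shell.
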